## **4 SUBJECT SELECTION AND ENROLLMENT**

Patient eligibility must be reviewed and documented by an appropriately qualified member of the investigator's study team before patients are included in the study. No exceptions to the patient eligibility requirements will be granted by the Sponsor.

### **4.1 Inclusion Criteria**

Patients must meet all of the following inclusion criteria as applicable for phase of the study to be eligible for enrollment into the study:

1. Diagnosis and disease status:
  - a. Phase 1 – Histologically or cytologically confirmed solid tumor malignancy with metastatic or unresectable, locally advanced disease
  - b. Phase 2 – Histologically confirmed NSCLC (any histology) with metastatic or unresectable, locally advanced disease
2. Prior treatments:
  - a. Phase 1
    - i. Not amenable to treatment with curative intent
    - ii. May have received treatment with checkpoint inhibitors (e.g., anti-PD-1 or anti-PD-L1)
  - b. Phase 2
    - i. Receipt of at least one prior treatment in the advanced disease setting that included a platinum-based doublet or immunotherapy regimen. If prior platinum-based therapy was received in the neoadjuvant or adjuvant setting, relapse must have occurred within 1 year of end of treatment.
    - ii. Cohorts 3 and 4 – Most recent treatment regimen must have included a checkpoint inhibitor, e.g., anti-PD-1 or anti-PD-L1 treatment.

3. Molecular analysis for PD-L1 expression on tumor cells:
  - a. Phase 1 – PD-L1 tumor expression testing is not required but is encouraged; any expression status is eligible
  - b. Phase 2
    - i. Cohorts 1 and 2 – Molecular analysis of tumor sample collected following most recent therapy, assessed using the PD-L1 (SP263) CDx assay. Inclusion in the treatment arms will be based on documented no/low PD-L1 expression (positivity < 25% of tumor cells) or high PD-L1 expression (positivity  $\geq$ 25% of tumor cells).
    - ii. Cohorts 3 and 4 – PD-L1 tumor expression testing is not required but is encouraged; any expression status is eligible.
4. Response to previous treatment with checkpoint inhibitor:
  - a. Phase 1 – Any response is eligible, as applicable.
  - b. Phase 2
    - i. Cohort 3 – clinical benefit (i.e., RECIST defined partial or complete response or stable disease for at least 16 weeks [+2 week window permitted for radiograph scheduling]) followed by radiographic progression of disease
    - ii. Cohort 4 – radiographic progression of disease  $\leq$  16 weeks after initiation of treatment (+2 week window permitted for radiograph scheduling)
5. Measurable disease
  - a. For Phase 1 – Measurable or evaluable, as per RECIST version 1.1
  - b. For Phase 2 – Measurable disease, as per RECIST version 1.1. Indicator lesions intended for repeat biopsy during the study should be excluded from selection as target lesions at baseline
6. Eastern Cooperative Oncology Group (ECOG) performance status 0 or 1
7. Adequate bone marrow and organ function demonstrated by:
  - a. Hemoglobin  $\geq$  9.0 g/dL
  - b. Absolute neutrophil count  $\geq$  1,500/mm^3 ( $\geq$  1.5  $\times$  10^9/L)

- c. Platelet count  $\geq 100 \times 10^9/L$  ( $\geq 100,000$  per  $\text{mm}^3$ )
  - d. Alanine aminotransferase (ALT) and aspartate aminotransferase (AST)  $\leq 2.5 \times$  Upper Limit of Normal (ULN), or  $\leq 5.0 \times$  ULN for patients with documented liver metastases
  - e. Serum bilirubin  $\leq 1.5 \times$  ULN or  $\leq 3.0 \times$  ULN for patients with Gilbert Syndrome or documented liver metastases
  - f. Serum creatinine  $\text{CL} > 40$  mL/min by the Cockcroft-Gault formula or by 24-hour urine collection for determination of creatinine clearance
8.  $\geq 18$  years of age
9. Women of child-bearing potential (WOCBP) or men whose partner is a WOCBP agrees to use contraception while participating in this study, and for a period of 6 months following termination of study treatment
10. Completed informed consent process, including signing IRB/EC-approved informed consent form
11. Willing to comply with clinical trial instructions and requirements

#### 4.2 Exclusion Criteria

Patients presenting with any of the following will not be included in the study:

1. Prior therapies:
  - a. All Cohorts
    - i. HDAC inhibitor for the treatment of the malignancy under study
    - ii. Immunotherapies not previously specified, including anti-CTLA-4, anti-OX40 and anti-CD137
  - b. Phase 2 Cohorts 1 and 2 – prior treatment with anti-PD-1 or anti-PD-L1
  - c. Phase 2 Cohorts 3 and 4 – receipt of systemic cancer treatments since progression of disease during or following administered checkpoint inhibitor
2. Patients with any history of tumors that test positive for *EGFR*, *ROS1*, *ALK* mutations or *ALK* fusions or any other mutations for which there are tyrosine kinase inhibitors available or under development.
3. Most recent prior therapeutic regimen discontinued  $\leq 3$  weeks before first study treatment dose date (i.e., mocetinostat Lead-in Period).

4. Lack of recovery from the adverse effects of prior therapy at the time of enrollment to  $\leq$  Grade 1 (excluding alopecia or neuropathy).
5. Previous treatment-related, severe ( $\geq$  Grade 3) AE or any neurologic or ocular AE of any grade while receiving checkpoint inhibitors. **NOTE:** Patients with a prior endocrine AE are permitted to enroll if they are stably maintained on appropriate replacement therapy and are asymptomatic.
6. Active or prior documented autoimmune disease within the past 2 years.  
NOTE: Patients with vitiligo, Grave's disease, or psoriasis not requiring systemic treatment (within the past 2 years) are not excluded.
7. Active or prior documented inflammatory bowel disease (e.g., Crohn's disease, ulcerative colitis).
8. Current or prior use of immunosuppressive medication within 28 days before the first dose of durvalumab, with the exceptions of intranasal and inhaled corticosteroids or systemic corticosteroids at physiological doses, which are not to exceed 10 mg/day of prednisone, or an equivalent corticosteroid.
9. Receipt of live attenuated vaccination within 30 days prior to study entry or within 30 days of receiving durvalumab.
10. History of primary immunodeficiency.
11. Known history of previous clinical diagnosis of tuberculosis.
12. Known history of acute or chronic hepatitis B, human immunodeficiency virus (HIV), or acute hepatitis C.
13. History of allogeneic organ transplant.
14. History of hypersensitivity to durvalumab, mocetinostat or any drug product excipient.
15. History of interstitial lung disease (ILD), drug-induced ILD, radiation pneumonitis which required steroid treatment, or any evidence of clinically active interstitial lung disease.
16. History of stroke or transient ischemic attack within the previous 6 months.
17. Any of the following cardiac abnormalities:
  - a. Unstable angina pectoris,
  - b. Congestive heart failure  $\geq$  NYHA Class 3,

- c. QTc  $\geq$ 470 milliseconds on electrocardiogram (ECG) calculated using Frediricia's Correction, or
  - d. Current or history of a small, moderate or large pericardial effusion, and/or hemodynamic compromise due to pericardial effusion of any size. Minimal or trivial pericardial effusion is not excluded.
18. Concomitant medication known to cause prolonged QT which cannot be discontinued or changed to a different medication prior to enrollment.
19. Active brain metastases. Subjects are eligible if brain metastases are adequately treated and subjects are neurologically stable (except for residual signs or symptoms related to the CNS treatment) for at least 2 weeks prior to enrollment without the use of corticosteroids, or on a stable or decreasing dose of  $\leq$  10 mg daily prednisone (or equivalent).
20. Known or suspected presence of another malignancy that could be mistaken for the malignancy under study during disease assessments.
21. Pregnancy. WOCBP must have a negative serum or urine pregnancy test documented within the screening period prior start of study drug.
22. Breast-feeding or planning to breast feed during the study or within 6 months after study treatment.
23. Any psychiatric illness/social situations that would limit compliance with study requirements or compromise the ability of the patient to give written informed consent.
24. Any serious illness, uncontrolled inter-current illness, active or uncontrolled infection, or other medical history, including laboratory results, which, in the Investigator's opinion, would be likely to interfere with the patient's participation in the study, or with the interpretation of the results.

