Amendment #2 Version 3.0 (cont'd)		
 
• Introduction and Rationale: 
 
○ Updated mocetinostat clinical data section for consistency with most recent version of mocetinostat Investigator’s Brochure (v9.0)
 
○ Updated durvalumab clinical data section and adverse events of special interest for consistency with most recent version of durvalumab Investigator’s Brochure (v10.0)
 
 
 
• Study Design: 
 
○ Added language for Phase 2 clinical activity evaluable population and included Predictive Probability Design (similar to Simon design, but allowing for more flexibility in the number of evaluable patients to take a decision on continuing or stopping additional patient enrollment) (page 52)
 
 
 
• Inclusion Criteria: 
 
○ Inclusion criteria #2 updated to include patients that have received either a platinum-based chemotherapy or an immunotherapy regimen based on changing standard of care for first line therapy
 
○ Inclusion criteria #2.b.ii deleted to exclude patients with tumors that test positive for EGFR mutation or ALK fusion
 
 
 
• Exclusion Criteria: 
 
○ Added Exclusion for Patients with any history of tumors that test positive for EGFR, ROS1, ALK mutations or ALK fusions or any other mutations for which there are tyrosine kinase inhibitors available or under development
 
○ Revised Exclusion #12 to include patients with a history of chronic hepatitis C that is no longer present
 
○ Revised Exclusion #17.c to allow for assessment from one ECG reading, as per Schedule of Assessments
 
○ Revised Exclusion #19 to note that subjects with active brain metastases are exclusionary. Subjects are eligible if brain metastases are adequately treated and subjects are neurologically stable (except for residual signs or symptoms related to the CNS treatment) for at least 2 weeks prior to enrollment without the use of corticosteroids, or on a stable or decreasing dose of ≤ 10 mg daily prednisone (or equivalent)
 
 
 
• Study Treatment: 
 
○ Updated Section 5.1.1 to add capsule strengths of 10 mg and 25 mg for mocetinostat study drug treatment (per Protocol Administrative Letter dated 05Jul16)
 
○ Updated Section 5.1.6 to provide further direction around mocetinostat administration and vomiting, as well as mocetinostat administration around PK sampling
 
 
 

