##### 3.1.1 Definition of Dose Limiting Toxicity

The National Cancer Institute Common Toxicity Criteria for Adverse Events (NCI CTCAE) version 4.03 will be used throughout this study. The definition of DLT includes any of the following events considered to be causally related to treatment with mocetinostat in combination with durvalumab:

- Any Grade 4 immune-related Adverse Event (irAE is defined in [Section 8.3.1](#))
- Grade 3 or greater colitis

- Grade 3 or greater noninfectious pneumonitis irrespective of duration
- Grade 2 pneumonitis that does not resolve to  $\leq$  Grade 1 within 3 days of the initiation of maximal supportive care
- Grade 3 irAE (excluding colitis or pneumonitis) that:
  - does not downgrade to Grade 2 within 3 days after onset of the event despite optimal medical management including systemic corticosteroids, or
  - does not downgrade to  $\leq$  Grade 1 or baseline within 14 days
- Liver transaminase elevation  $> 8 \times$  ULN or total bilirubin  $> 5 \times$  ULN
- Grade 3 or greater non-irAE, except for the exclusions listed below:
  - Nausea, vomiting, anorexia, dehydration, or diarrhea that can be managed with typical medical interventions

The definition of DLT excludes the following conditions:

- Grade 3 fatigue lasting  $\leq 7$  days
- Grade 3 endocrine disorder (thyroid, pituitary, and/or adrenal insufficiency) that is managed with or without systemic corticosteroid therapy and/or hormone replacement therapy and the patient is asymptomatic
- Grade 3 inflammatory reaction attributed to a local antitumor response (e.g., inflammatory reaction at sites of metastatic disease, lymph nodes, etc)
- Concurrent vitiligo or alopecia of any grade
- Grade 3 infusion-related reaction (first occurrence and in the absence of steroid prophylaxis) that resolves within 6 hours with appropriate clinical management
- Grade 3 or 4 neutropenia that is not associated with fever or systemic infection that improves by at least 1 grade within 3 days. Grade 3 or Grade 4 febrile neutropenia will be a DLT regardless of duration or reversibility
- Grade 3 or 4 lymphopenia
- Grade 3 thrombocytopenia that is not associated with clinically significant bleeding that requires medical intervention, and improves by at least 1 grade within 3 days

- Isolated Grade 3 electrolyte abnormalities that are not associated with clinical signs or symptoms and are reversed with appropriate maximal medical intervention within 3 days

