**Table 9: Immune-Related Adverse Events, Overall Management (Continued)**

**Toxicity Management**

- Patients should be thoroughly evaluated to rule out any alternative etiology (e.g., disease progression, concomitant medications, infections, etc.)
- In the absence of a clear alternative etiology, all events should be considered potentially immune related
- Symptomatic and topical therapy should be considered for low-grade (Grade 1 or 2, unless otherwise specified) events
- For persistent (greater than 3 to 5 days) low-grade (Grade 2) or severe (Grade  $\geq 3$ ) events promptly start prednisone PO 1-2mg/kg/day or IV equivalent
- If symptoms recur or worsen during corticosteroid tapering 28 days of taper), increase the corticosteroid dose (prednisone dose [e.g., up to 2-4mg/kg/day or IV equivalent]) until stabilization or improvement of symptoms, then resume corticosteroid tapering at a slower rate ( $\geq 28$  days of taper)
- More potent immunosuppressives such as TNF inhibitors (e.g., infliximab) – should be considered for events not responding to systemic steroids (also refer to the individual sections of the immune related adverse event for specific type of immunosuppressive)
- Discontinuation of study drug is not mandated for Grade 3 / Grade 4 inflammatory reactions attributed to local tumour response (e.g., inflammatory reaction at sites of metastatic disease, lymph nodes etc.). Continuation of study drug in this situation should be based on a benefit/risk analysis for that patient

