## **Definition of Terms**

**Life threatening:** An AE is life threatening if the patient was at immediate risk of death from the event as it occurred; i.e., it does not include a reaction that if it had occurred in a more serious form might have caused death. For example, drug-induced hepatitis that resolved without evidence of hepatic failure would not be considered life-threatening even though drug-induced hepatitis can be fatal.

**Hospitalization:** In general, hospitalization signifies that the patient has been detained (usually involving at least an overnight stay) at the hospital or emergency ward for observation and/or treatment that would not have been appropriate in the physician's office or outpatient setting. When in doubt as to whether 'hospitalization' occurred or was necessary, the AE should be considered serious. Hospitalization for elective surgery or routine clinical procedures that are not the result of AE (e.g., elective surgery for a pre-existing condition that has not worsened) need not be considered AEs or SAEs. If anything untoward is reported during the procedure, that occurrence must be reported as an AE, either 'serious' or 'non-serious' according to the usual criteria.

**Disability/permanent damage:** An AE is disabling or caused permanent damage if it resulted in a substantial disruption of a person's ability to conduct normal life functions, e.g., a significant, persistent or permanent change, impairment, damage or disruption in body function/structure, physical activities and/or quality of life.

**Adverse Event of Special Interest (AESI):** AESIs are of scientific and medical interest specific to understanding of the Investigational Product and may require close monitoring and rapid communication by the investigator to the sponsor. An AESI may be serious or non-serious. The rapid reporting of AESIs allows ongoing surveillance of these events in order to characterize and understand them in association with the use of this investigational product.

**Immune-related Adverse Events (irAE):** An irAE is defined as an adverse event that is associated with drug exposure and is consistent with an immune-mediated mechanism of action and where there is no clear alternate aetiology. Serologic, immunologic, and histologic (biopsy) data, as appropriate, should be used to support an irAE diagnosis. Appropriate efforts should be made to rule out neoplastic, infectious, metabolic, toxin, or other etiologic causes of the irAE.

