#### Appendix 4 Management of Specific Immune-Related Adverse Events (Continued)

Hepatitis (Elevated LFTs)		

 
• Infliximab should not be used for management of Immune Related Hepatitis
 
• Monitor and evaluate liver function test: AST, ALT, ALP and total bilirubin
 
• Evaluate for alternative etiologies (e.g., viral hepatitis, disease progression, concomitant medications)
 
		
Grade of AE	Dose Modifications	Toxicity Management
Grade 1 (AST or ALT > ULN to 3 times ULN and/or TB > 1.5 times ULN)	
 
• None required
 
• If it worsens, treat as Grade 2 event
 
	
 
• For Grade 1 AST or ALT and/or TB elevation
 
• Continue LFT monitoring per protocol
 

Grade 2 (AST or ALT > 3-5 times ULN and/or TB > 1.5-3.0 times ULN)	
 
• Hold dose until Grade 2 resolution to <math>\leq</math> Grade 1
 
• If worsens then treat as Grade 3 or Grade 4
 
• If improves to <math>\leq</math> Grade 1 or baseline resume study drug/study regimen after completion of steroid taper.
 
	
 
• For Grade 2 AST or ALT and or TB elevation - Frequent checking of LFTs (e.g. every 1-2 days) until elevations improving or resolved.
 
• If no resolution in 1-2 days, discuss with study physician.
 
• If event is persistent (> 3-5 days) or worsens, promptly start prednisone 1-2 mg/kg/day PO or IV equivalent.
 
• If still no improvement within 3-5 days despite 1-2 mg/kg/day of prednisone PO or IV equivalent, consider additional workup and prompt treatment with IV methylprednisolone 2-4 mg/kg/day started.
 
• If still no improvement within 3-5 days despite 2-4mg/kg/day of IV methylprednisolone, promptly start immunosuppressives (mycophenolate mofetil). Discuss with study physician if mycophenolate mofetil is not available. Infliximab should NOT be used.
 
• Once improving, gradually taper steroids over <math>\geq</math> 28 days and consider prophylactic antibiotics, antifungals and anti PCP treatment (refer to current NCCN guidelines for treatment of cancer-related infections [Category 2B recommendation])
 

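### Exclusion 12 bars only acute hepatitis C, so a patient with known, active chronic hepatitis C and no recorded acute episode meets no mandatory exclusion, which clouds attribution of liver events

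*Protocol*

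**What the plan says.** Protocol Section 4.2, criterion 12, excludes "Known history of acute or chronic hepatitis B, human immunodeficiency virus (HIV), or acute hepatitis C". No other inclusion or exclusion criterion names hepatitis C.

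Two other criteria bear on such a patient. Exclusion 24 covers "active or uncontrolled infection, or other medical history, including laboratory results, which, in the Investigator's opinion, would be likely to interfere" with participation or with interpretation of the results. Inclusion 7 sets laboratory limits, among them "Alanine aminotransferase (ALT) and aspartate aminotransferase (AST") up to 2.5 × ULN (5.0 × ULN with liver metastases), bilirubin up to 1.5 × ULN (3.0 × ULN with Gilbert syndrome or liver metastases) and platelets of at least 100 × 10⁹/L. Neither the Schedule of Assessments (Table 1) nor the laboratory panel (Table 13) includes a viral hepatitis test.

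The rules for attributing liver events are spread over several places:

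- Appendix 4, hepatitis table: "Evaluate for alternative etiologies (e.g., viral hepatitis, disease progression, concomitant medications").
- Table 9, toxicity management: "Patients should be thoroughly evaluated to rule out any alternative etiology (e.g., disease progression, concomitant medications, infections, etc.)"
- Section 8.3.1, definition of an immune-related event: "Appropriate efforts should be made to rule out neoplastic, infectious, metabolic, toxin, or other etiologic causes of the irAE".
- Appendix 4, Grade 3 hepatitis row: the Hy's law discontinuation rule applies when there is no alternative cause.
- Section 3.1.1: "Liver transaminase elevation" above 8 × ULN, or total bilirubin above 5 × ULN, is a DLT if judged causally related to the combination.
- Section 3.1.4: the recommended Phase 2 dose must show no related immune event that is serious or of Grade 3 or higher.

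The Document History states what the Amendment 2 change to this criterion was for: "Revised Exclusion #12 to include patients with a history of chronic hepatitis C that is no longer present".

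**The concern.** Criterion 12 separates acute from chronic disease for hepatitis B, so the word acute cannot be read as silently covering chronic disease for hepatitis C. Read literally, the criterion leaves chronic hepatitis C, active or resolved, outside its scope.

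Hepatitis is an adverse event of special interest for durvalumab. The liver rules work only if the site can separate a treatment cause from a viral one. In a patient with active hepatitis C, a competing viral cause is present from baseline, so a transaminase rise is hard to assign. The error can go either way: a viral event may be recorded as treatment-related, or an immune hepatitis may be put down to the virus. In Phase 1 this could affect the DLT count and the choice of Phase 2 dose. In Phase 2 it could affect the related-event and immune-event tables.

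**Working it through.** No arithmetic applies, and the plan states no figure on this point to reproduce. The check is to apply criterion 12 as written to each kind of known hepatitis C history, and then to see which other rule would act.

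**Step 1. Apply criterion 12.**

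| Known hepatitis C history | Excluded by criterion 12? |
|---|---|
| Acute episode recorded, since cleared | Yes |
| Acute episode recorded, now chronic and active | Yes |
| Chronic and active, no acute episode recorded | No |
| Chronic, no longer present, no acute episode recorded | No |

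The criterion sorts patients by whether an acute episode was ever recorded, not by whether infection is present now. The third row is the gap.

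**Step 2. Look for another rule that catches the third row.**

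- Inclusion 7 limits enzymes, bilirubin, platelets and other values. It does not address infection, so a patient within those limits passes.
- Exclusion 24 could be used, but it does not name hepatitis C, does not say whether a stable chronic infection counts as active or uncontrolled, and refers to the investigator's opinion. It allows exclusion without securing it, and sites may differ.
- Tables 1 and 13 contain no hepatitis test, so no scheduled result would prompt a second look.
- Sections 4 and 13.2 state that the sponsor grants no eligibility exceptions, so sites depend on the wording. The first-row patient cannot be admitted by waiver.

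**Step 3. Compare with the attribution rules.**

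- The hepatitis table in Appendix 4 asks sites to evaluate for viral hepatitis. Table 9 and the definition in Section 8.3.1 go further and speak of ruling out infectious causes. In a third-row patient an infectious cause is already known to exist.
- The Hy's law rule in Appendix 4 depends on the absence of an alternative cause. In this patient one is always arguable.
- Section 8.2.3 has an investigator who does not know whether treatment caused an event report it as related. An unclear liver event therefore goes to the treatment by default.
- That judgement feeds the liver DLT criterion in Section 3.1.1 and the Phase 2 dose condition in Section 3.1.4, both of which turn on causality.

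**Step 4. Size.** The number of affected patients would be the prevalence of known active chronic hepatitis C without a recorded acute episode, multiplied by enrolment. The documents give no prevalence, so no figure follows.

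**The case against.** The strongest reply is that a safeguard already exists. Exclusion 24 names active or uncontrolled infection and medical history likely to interfere with interpreting the results, and clouded liver attribution is such an interference. It is also unclear whether the reference to the investigator's opinion governs the whole list or only its last item. This stands in part: enrolment of such a patient is possible, not assured. It does not close the gap, because the one criterion that deals with hepatitis by name leaves chronic hepatitis C out.

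A second reply is that Appendix 4 already tells sites to look for viral hepatitis when liver tests rise, so the differential is anticipated. That is correct. But looking for a cause does not resolve attribution when the cause was known at entry.

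Some stronger readings are tempting but unsupported:

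- *The criterion admits the infected and rejects the cleared.* This is not true in general. It also admits resolved chronic hepatitis C, and it excludes an actively infected patient who has a recorded acute episode.
- *One misattributed liver event changes the dose decision.* In Appendix 2, going from 1 to 2 DLTs among 6 patients leaves the decision at stay. Where a decision does change, it would do so for any misattributed event, so it does not measure this gap.
- *All Phase 2 patients, up to 261, are affected.* That figure is an enrolment ceiling, not a count of patients with hepatitis C.
- *The sponsor deliberately permits active chronic disease, or the Document History contradicts the criterion.* Nothing in the text shows deliberate permission. A log entry that differs from current text is not itself an error; here it serves only as evidence of purpose.
- *Enrolled patients will suffer viral flares or worse liver outcomes.* The documents contain no data on this.

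**Conclusion.** The gap is real and follows from the current wording of criterion 12 alone. A patient with known active chronic hepatitis C, no recorded acute episode and values within Inclusion 7 meets no mandatory exclusion, while a past, cleared acute infection is excluded. The protocol's own attribution rules are harder to apply in the first patient, with possible effects on liver DLTs, on the Phase 2 dose condition and on immune-event reporting.

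The size cannot be stated. It depends on a prevalence the documents do not give and on how often investigators would use Exclusion 24, and it may be small. The conclusion assumes that sites apply criterion 12 as written. The response-rate endpoint, error rates and decision boundaries are unaffected. This is a should-fix.

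**What to change.** Reconcile criterion 12 with the attribution rules in Appendix 4, Table 9 and Section 8.3.1, and with the purpose recorded for it in the Document History. The direct way is to reword the hepatitis C part so that eligibility turns on whether known infection, acute or chronic, is currently present, with past infection documented as no longer present being eligible. The hepatitis B and HIV parts can stay as they are.

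The cost is one sentence in an amendment. Because the criterion stays on known status, no new screening test is needed. A few patients with known active chronic hepatitis C become ineligible, and a few with a cleared acute infection become eligible. Undiagnosed infection would still go undetected and could still confound a liver event; the rewording does not claim to solve that.
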